## Statement of Compliance

This study will be conducted in accordance with the International Conference on Harmonisation guidelines for Good Clinical Practice (ICH E6), the Code of Federal Regulations on the Protection of Human Subjects (45 CFR Part 46), and Thomas Jefferson University research policies

---

## List of Abbreviations

AA: African American

ASCO: American Society of Clinical Oncology

*BRCA1, BRCA2, ATM, PALB2, CHEK2, NBN*, the DNA mismatch repair genes: cancer risk genes

GEM: Genetic Evaluation of Men

GU: Genitourinary

MEE: Motivational, Educational, Entertainment Productions, Philadelphia, PA

NCCN: National Comprehensive Cancer Network

PARP: Poly ADP ribose polymerase

PCA: Prostate cancer

RESPOND: Research on Prostate Cancer in Men of African Ancestry

SURE: Decisional conflict scale

TPB: Theory of Planned Behavior

US: United States

## Study Summary

[figure not shown]
Title:	Peer-Based Intervention for Genetic Evaluation for Prostate Cancer among African American Men: The Peer Genetic Study
Précis:	The study will evaluate the impact of a peer-educator led, clinic-based intervention to educate men about their risk of prostate cancer and facilitate genetic testing for prostate cancer risk assessment
Objectives:	
Aim 1: Explore barriers to genetic testing and opportunities for intervention among AA males who live in low-resource communities through focus groups with AA men and interviews with key stakeholders.
 
Aim 2: Implement a community-based peer health education intervention. AA male peer health educators will be trained in PCA genetics, and a randomized trial will be implemented for 176 AA males in the community of peer health education vs. mailed informational materials.
 
Aim 3: Evaluate the impact of peer health education. The primary outcome will be decisional conflict regarding consideration of genetic testing. Exploratory outcomes will include rates of AA men meeting NCCN genetic testing guidelines and assessment of genetic counseling experience among AA men who opt for genetic testing.

Population:	176 men will be randomized to receive either: (1) a peer-led, clinic based educational intervention or (2) standard written materials about personal and family history of prostate cancer. Eligible men are between the ages of 35-69 and can speak and read English comfortably.
Phase:	N/A: Randomized controlled trial of a behavioral intervention
Number of Sites:	CityLife Neighborhood Clinic [name]  AND

---

Community and Church based organizations in and around Philadelphia, PA

Description of Intervention:	Men in the intervention group (n=88) will attend a peer-led education session about PCA genetic testing while men in the control group (n=88) will receive mailed informational materials about PCA genetic testing. Men in either group who wish to pursue genetic testing will be referred to the Clinical Cancer Genetics Program at SKCC. The cost of genetic testing will be covered for all men.
Study Duration:	4 years: July 1, 2019- June 30, 2024
Participant Participation Duration:	Estimated time is 1-3 months
Estimated Time to Complete Enrollment:	3.5 years (April 2020-October 2023)

### Schematic of Study Design:

## 1 Introduction

### 1.1 Background Information

African American (AA) males have some of the highest rates of prostate cancer (PCA) incidence and death in the US. Indeed, AA males have over twice the rate of mortality from PCA compared to any other race group. While the causes of this disparity in PCA mortality for AA men likely include a combination of biologic, behavioral, and environmental factors, a deep understanding of the interplay of these factors lending to PCA-related death remain largely unknown. In fact, a major study as part of the Cancer Moonshot led by the National Cancer Institute, National Institute of Minority Health and Health Disparities, and Prostate Cancer Foundation (RESPOND - Research on Prostate Cancer in Men of African Ancestry) is now underway to gain greater understanding of PCA aggressiveness among AA men. Thus, reducing PCA disparities for AA men is now taking major national priority. To maximize the impact of such studies will require novel groundwork in community settings.

Meanwhile, genetic testing is revolutionizing PCA care. Over the last 2-3 years, research studies have provided ground-breaking insights into high rates of germline (inherited) mutations (12-15%) among men with metastatic PCA. Our research group extended the scope of insights into inherited genetic mutations, reporting rates of 5-7% among men with earlier stage PCA particularly with strong family cancer history. Mutations in multiple genes have been reported in these prior studies including *BRCA1*, *BRCA2*, *ATM*, DNA mismatch repair genes, *NBN*, and *CHEK2*. Furthermore, men with PCA and specific genetic mutations have been shown to have improved responses to targeted therapy with PARP inhibitors, leading the FDA to grant “Breakthrough Therapy” designation for olaparib (a PARP inhibitor) for men with *BRCA1*, *BRCA2*, or *ATM* mutations. These landmark insights led our institution to host and publish the first international consensus conference on the “Role of Genetic Testing for Inherited Prostate Cancer Risk” to set forth a comprehensive framework for genetic testing for men with PCA. Subsequently, the National Comprehensive Cancer Network (NCCN) rapidly expanded genetic testing guidelines to encompass testing multiple genes including *BRCA1*, *BRCA2*, *ATM*, *PALB2*, *FANCA*, and DNA mismatch repair genes in all men with metastatic PCA, men with earlier stage disease who have strong family cancer history, or men unaffected with PCA who are making screening decisions and have a strong family cancer history. Thus, genetic results are now informing precision treatment for metastatic PCA, management for early-stage disease, and PCA screening discussions among men unaffected with PCA.

*A major concern is that expansion of genetic testing for PCA will increase PCA disparities for AA men.* In fact, genetic information in AA men is a major gap in knowledge due to low representation in prior genetic studies. Patients from ethnic minority groups participate less frequently in genetic testing due to lack of awareness or understanding, cultural beliefs, financial limitations, fear of discrimination, and mistrust in the healthcare system. This is of particular concern in the Philadelphia region, where African Americans account for up to 44% of our catchment area, and PCA mortality exceeds the national average. Addressing awareness, barriers to consideration of genetic evaluations, and engagement in informed decision-making for genetic testing for PCA among AA men is therefore imperative, since testing is increasingly informing screening strategies for unaffected men and treatment for men with PCA.

Peer health education has been used to access ‘hard to reach’ groups with the participation of those who are of a similar age, background or interest. Typically, there are four essential elements of peers: (1) they share specific characteristics, experiences, or circumstances and are selected because they are from the same community or belong to a specified subgroup; (2) their shared qualities increase the effectiveness of the services they provide; (3) they lack professional training or status in the scope of their work, but are trained to deliver a specific intervention; and (4) they function intentionally based on standardized protocols, and therefore their interactions extend beyond their existing social network. Peer-led dialogue groups have the potential to increase families' and communities' uptake of recommended health practices. Facilitated discussions allow group members to actively participate in the learning process and share their experiences and knowledge with other group members, as well as engage in group problem-solving. Hearing what group members know, think, and do can lead other members to positively change their attitudes and behaviors. The use of peer interventions has been demonstrated as effective, regardless of the health behavior, the population or demographics of individuals who are the target audience, although most have been related to HIV testing, alcohol and substance abuse, physical activity, heart disease, and diabetes.

## 1.2 Rationale for the Proposed Study

As an increasing number of people seek information about cancer genetics, there is a growing need for competent and culturally relevant dissemination of information. It is well documented that low-income, low-literacy individuals are less likely to participate in genetic counseling and genetics research, which only continues to perpetuate health disparities. Previous research indicates that individuals with reduced health literacy often report feeling overwhelmed during a genetic counseling session due to too much information, the complexity of the information, unintentional inhibition of patient engagement and interaction, and vague discussions about screening and testing resources. Peer-led programs are uniquely suited to fill part of this gap by educating individuals about basic cancer genetics in a way that is understandable and relatable for those involved.

The proposed study titled “Peer-Based Intervention for Genetic Evaluation for Prostate Cancer among African American Men: The Peer Genetic Study” will identify and address barriers and beliefs regarding genetic testing for PCA among AA men in the Philadelphia region. The study will build upon strong community partnerships supported by prior DOD funding and link to a first-in-field genetic counseling and genetic testing program. Leveraging an invested cadre of AA male peer health educators, the study will train them in the principles and practice of genetic testing, to implement a peer education intervention in a community clinic setting. We aim to study the impact of peer education, compared to the standard approach of printed educational materials, in reducing decisional conflict about genetic testing. Results of the study will inform health system approaches and health policy, regarding peer education. We expect the results to ultimately reduce PCA disparities for AA men by promoting responsible engagement in informed decision-making for genetic testing to guide PCA screening and treatment. Therefore, the study will create a community-based sustainable pipeline to address the overarching challenge of engaging AA males in cancer genetics research to define the biology of lethal prostate cancer, namely germline genetics of AA men. Results of the study will ultimately inform PCA screening and identification of novel targeted agents for population-specific precision treatment of PCA to reduce death among AA men.

### 1.3 Previous Research

The current proposal leverages expertise in clinical cancer genetics, PCA risk assessment, PCA treatment, community-based health interventions, and population science towards the goal of developing, implementing, and assessing a novel peer-based PCA genetic education program for AA males in community health clinics. Limited genetic data has hindered tailored PCA screening and the development of targeted therapies to improve PCA outcomes in AA men, necessitating novel approaches to genetic evaluation for AA men as proposed here.

**Leadership in prostate cancer genetic testing.** [name] is a medical oncologist with specialization in clinical cancer genetics. She has been a thought leader in conducting multigene testing for inherited PCA through the Genetic Evaluation of Men (GEM) study (Partially funded by PA Department of Health grant). [name] started the first Men’s Genetic Risk Clinic in the US in 2014 focused on genetic evaluation of inherited PCA. [name] also co-chaired an international consensus conference that published a comprehensive framework for genetic evaluation of PCA, which noted that genetic testing among AA males is a high priority due to lack of genetic data in this population. [name] work has contributed novel insights into the germline spectrum of inherited PCA from multigene testing. Furthermore, [name] and [name] collaborated on a project of understanding of genetic test results among men and co-authored the publication.

**Forefront of community-based PCA education for African Americans.** [name] is a population scientist and a current recipient and Co-PI of a Synergistic IDEA Award (#PC140667) (Title: *A Neighborhood Based Intervention to Reduce PCA Disparities*) (Funded 10/15-9/18). [name] is a Co-Investigator on the funded study. Specific Aims for the funded study were to: (1) identify neighborhoods with disproportionately high rates of advanced PCA and describe patient- and neighborhood-level risk factors associated with the high-risk neighborhoods; (2) develop, using a mixed methods approach, a peer-led educational intervention about PCA for men who live in high risk neighborhoods; (3) test the impact of the intervention on levels of knowledge, anxiety, and informed decision making about PCA screening; (4) observe rates of PCA screening in the intervention and control groups. The research team successfully enrolled 240 AA males into this study, demonstrating its ability to engage and collaborate with the AA communities of Philadelphia.

**Collaboration of successful prior research and expertise for the current proposal.** The PI ([name]) and Co-PI ([name]) will now leverage their successful experience with genetic education and counseling, genetic testing, and community-based research toward addressing barriers and developing implementation of genetic evaluation for PCA for AA males from community health clinics in underserved communities in the Philadelphia area, which has some of the highest burden of lethal PCA in the US. The specific aims of the current proposal are designed to gain information on challenges and barriers to uptake of genetic assessment for PCA among AA males, develop a peer education intervention for community health clinics with predominantly AA population, and assess the value of peer education in decisional conflict to seek genetic testing. Knowledge gained from implementing Study # PC140667 will ensure the likelihood of success of the proposed study in the following ways: (1) We have engaged a diverse group of community partners to form a network of grass-roots and professional organizations which will form the foundation of community engagement and outreach crucial for its success; (2) We developed a specialized curriculum for training peer health educators, which will serve as the foundation for training the peer health educators in PCA genetic assessment for the proposed study; (3) Five peer health educators from # PC140667 will be readily trained and engaged in the proposed study. Thus, the current proposal will make major strides to addressing barriers to awareness and implementation of genetic evaluation for AA males to ultimately reduce death from PCA.

## 1.4 Potential Risks and Benefits

### **1.4.1 Potential Risks**

There are very few risks expected with this educational intervention. Participants may experience anxiety when talking or thinking about their personal or family risk of cancer. There may be a loss of confidentiality when discussing your medical history with a peer health educator. All efforts to reduce these risks, whether psychosocial or privacy-related, will be taken.

### **1.4.2 Benefits**

Potential benefits to patients include learning more about PCA and how one's personal or family history of disease may increase one's risk of PCA. Also, having access to genetic testing may benefit some participants.

## **2 Study Objectives**

### **2.1 Study Aims**

Aim 1: Explore barriers to genetic testing and opportunities for intervention among AA males who live in low-resource communities through focus groups with AA men and stakeholders.

Aim 2: Implement a PCA genetics education and testing program for AA men who live in low-resource communities. Eligible men will be randomized to either the intervention group (peer-led health education sessions) or the control group (mailed materials).

Aim 3: Evaluate the impact of the intervention. The primary outcome is decisional conflict regarding consideration of genetic testing. Exploratory outcomes include rates of AA men meeting NCCN genetic testing guidelines and assessment of genetic counseling experience among AA men.

### **2.2 Endpoints/Outcome Measures**

Aim 1: Focus groups will uncover knowledge and awareness of prostate cancer; understanding of genetic testing; perceptions of genetic testing; risks and benefits of testing

Aim 2: Outcome will be the design of a feasible intervention to employ in a community-practice setting.

Aim 3: Analysis of intervention data will determine: extent of decisional conflict; knowledge of prostate cancer and genetic testing for prostate cancer risk; individual assessment of prostate cancer risk; intentions to seek genetic testing (if appropriate)

### 3 Study Design

#### 3.1 Characteristics

Aim 1: Two focus groups consisting of men who are current patients of CityLife Neighborhood Clinic or who live in the surrounding neighborhood

Aim 2/3: Design and implementation of an educational intervention to increase knowledge about PCA, the role of personal and family history as risk factors for PCA, and the purpose of genetic testing for PCA risk, if appropriate.

#### 3.2 Number of Participants

Aim 1: 2 focus groups, each with 8-10 men

Aim 2/3: 176 men

#### 3.3 Duration of Study Intervention

Aim 1: Each focus group will last approximately 1.5 hours

Aim 2/3: Each participant will be in the study for approximately 2 months

### Treatment Assignment Procedures

#### 3.3.1 Randomization Procedures

Aim 2/3: At the time of consent and enrollment into the study, each participant will be randomly assigned to participate in the intervention arm or the control arm. A randomization scheme will be provided by the study biostatistician.

#### 3.4 Study Timeline

	Year 1				Year 2				Year 3			
Convene Advisory Board	x	x	x	x	x	x	x	x	x	x	x	x

IRB Approval of Study	x												
Conduct Focus Groups and Stakeholder Interviews		x											
Recruit and Train Peer Health Educators			x										
Develop Intervention Materials			x										
Implement Intervention; Refer to Genetic Testing				x	x	x	x	x	x				
Data Cleaning and Analysis										x	x		
Disseminate Study Results												x	x

## 4 Study Enrollment and Withdrawal

### 4.1 Eligibility Criteria

#### 4.1.1 Inclusion Criteria

Aim 1: Men will be eligible to participate in a focus group if they are between the ages of 35 and 69 and are able to read and speak English comfortably. Men with or without a personal or family history of PCA are eligible to participate in a focus group. Men do not need to be an established patient at CityLife Neighborhood Clinic in order to participate in a focus group.

Aim 2/3: Men will be eligible to participate in the intervention if they are between the ages of 35 and 69 and are able to read and speak English comfortably. Men with or without a personal or family history of PCA are eligible to participate. Men do not need to be an established patient at CityLife Neighborhood Clinic in order to participate.

#### 4.1.2 Exclusion Criteria

Aim 1: Men who are not between the ages of 35 and 69, or who do not read or speak English comfortably will not be able to participate in a focus group.

Aim 2/3: Men who are not between the ages of 35 and 69, or who do not read or speak English comfortably will not be able to participate in the intervention. Additionally, men who participated in a focus group will be excluded from participating in the intervention.

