**Participant Recruitment and Study Enrollment.** MEE Productions, Inc. will develop culturally-tailored recruitment materials including flyers, posters and email blasts for CityLife Clinics to send to their AA male patients. The goal is to enroll 176 men in the study. We are anticipating a roughly 15% attrition rate over the course of the intervention, producing a final sample size for analysis of 150 men. We anticipate, based on our previous experience in community-based research, that we will have to screen about 10 times that number, or about 2000 men, to reach our study recruitment goal of 176 men. The research team will work with CityLife Clinic to mail a study recruitment letter to eligible males at their clinic, inviting them to participate. A toll-free, local telephone number will be included in the letter for men to opt-out of the study. After two weeks, any male who has not opted out will receive a telephone call from a member of the research team to screen for study eligibility. We will supplement our recruitment at CityLife Clinic by grassroots outreach in the neighborhood surrounding the clinic, to invite men not associated with the clinic to participate. We will promote the study at community recreation centers, public libraries, housing complexes and apartments, local non-profit organizations, barbershops, and employment agencies. Men who see the flyers or a member of the study team in the community can also call the toll-free, local number to screen for eligibility and participate. This is a similar approach that the study team was successful in using for the previously funded DOD study.

**Study eligibility.** Men who call the telephone number associated with the study or are who approached in the community will be screened for eligibility by the study research manager. Any AA male with or without prostate cancer between the ages of 35-69 will be eligible for the study. Men must speak and read English comfortably, as all study materials will be in English. Men do not need to be established patients at CityLife Clinics to participate.

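### Men who have already had germline testing can be randomised, although the decision the primary outcome measures is closed for them

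*Combined protocol and SAP*

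**What the plan says.** Section 4.1.1 limits Aim 2/3 by age (35 to 69) and English, and adds: "Men with or without a personal or family history of PCA are eligible to participate". The study eligibility paragraph in section 6 adds race and repeats the openness to affected men: "Any AA male with or without prostate cancer between the ages of 35-69 will be eligible for the study".

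Section 4.1.2 restates the age and language limits and gives one exclusion based on earlier exposure: "Additionally, men who participated in a focus group will be excluded from participating in the intervention".

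Section 1.1 says NCCN guidelines have been widened to cover multigene testing "in all men with metastatic PCA, men with earlier stage disease who have strong family cancer history", and also unaffected men with a strong family history who are making screening decisions.

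The baseline survey (section 6) lists knowledge, family cancer history, attitudes, norms, decisional conflict, intentions, demographics and other health information. Prior germline testing is not a listed item. Section 9.2 makes the two-month change in SURE score the primary outcome, compared by intention to treat, and lists testing and counselling intentions and uptake among the additional analyses.

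**The concern.** The hypothesis in section 9.1 is about conflict over a decision to seek testing. It presumes that the decision is open. The eligibility rules do not require this, and by admitting men with prostate cancer while citing guidelines that already call for testing some of them, they leave a clear route for tested men to enter.

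For such a man the first SURE item refers to a choice already made. His intention to be tested has no clear meaning. His uptake is worse: if he does not call the genetics program, he looks the same as a man who weighed testing and declined.

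Two things are at stake. The difference between arms shrinks towards zero, in a design with no spare power. And intentions and uptake, which the plan analyses as intervention effects, mix declined with already done. Because prior testing is not a listed item, the analyst could not be sure of finding these men afterwards.

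**Working it through.** **Inputs.** From section 9.3: difference 0.40, SD 0.76, two-sided alpha 0.05, 90% power, 75 per group, 88 per arm enrolled, about 15% attrition. The SD given there describes scores, while the primary analysis uses changes; like the plan, I use 0.76 throughout. The share f of randomised men already tested is not in the documents, so 5% and 10% are assumptions. They correspond to 0.05 × 176 = 8.8 (about 9) and 0.10 × 176 = 17.6 (about 18) men.

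**1. The plan's own figure.**
- n per arm = 2 × (1.960 + 1.282)² × 0.76² / 0.40² = 2 × 10.51 × 0.5776 / 0.16 = 75.9, so 76 (77 by exact t-test) against 75 stated.
- Power at 75 per arm: standard error 0.76 × √(2/75) = 0.124; 0.40 / 0.124 = 3.22; Φ(3.22 − 1.96) = 0.897. The exact t-test gives 0.893.
- Enrolment: 150 / 0.85 = 176.5, so 177 against 176 stated.

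The design reproduces within rounding, at about 89% power.

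**2. Dilution with the SD held at 0.76.** If a share f shows no intervention effect, the mean difference is 0.40 × (1 − f). By t-test at 75 per arm:
- f = 5%: 0.38, power 0.860
- f = 10%: 0.36, power 0.822

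**3. Dilution with zero change for these men.** Men whose score does not move also reduce the spread. Take SD 0.76 and mean change 0 (control) or 0.40 (intervention) among the other men, and exactly zero change for the share f. Then:
- control variance = (1 − f) × 0.5776
- intervention variance = (1 − f) × 0.5776 + f(1 − f) × 0.16

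| f | Control variance | Intervention variance | Pooled SD | Difference / SD | Power |
|---|---|---|---|---|---|
| 5% | 0.5487 | 0.5563 | 0.743 | 0.511 | 0.875 |
| 10% | 0.5198 | 0.5342 | 0.726 | 0.496 | 0.855 |

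The loss is therefore about 2 to 3 points at 5% and about 4 to 7 points at 10%. Both versions assume that a tested man cannot move at all. That is pessimistic, because three of the four SURE items ask about knowing benefits and risks, clarity about what matters, and support, and education could still shift those.

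**4. Can the planned analyses recover this?** Section 9.2 offers ANCOVA if baseline imbalance causes concern, and a look at effect modification in subgroups. Neither can isolate men whose testing status is not a listed variable, and adjusting for baseline SURE does not separate a tested man from an untested man who is simply sure.

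**The case against.** The strongest reply is that few such men are likely to enrol. Section 1.1 says ethnic minority groups take part in genetic testing less often and describes the guideline expansion as recent. The protocol also chose to admit men with and without prostate cancer, and says so twice. The surveys are not yet part of the document (see the Appendices), so a prior-testing question may appear there. And excluding tested men would tend to remove men who meet NCCN criteria, pulling down the exploratory NCCN proportion. All of this stands. It limits the size of the problem and shapes the fix. It does not close the gap, because a survey item is not an eligibility rule.

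Two wider readings are tempting, and the documents do not support either.

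*That counselled men have also already decided.* Under Referral to Genetic Counseling in section 6, the counselling visit comes before the man agrees to testing. A man who was only counselled may still have an open decision.

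*That men from the team's earlier study must be excluded as well.* Section 1.3 reports that "The research team successfully enrolled 240 AA males into this study", which developed "a peer-led educational intervention about PCA for men who live in high risk neighborhoods". It adds that "Five peer health educators from # PC140667 will be readily trained and engaged in the proposed study", and section 6 says of recruitment: "This is a similar approach that the study team was successful in using for the previously funded DOD study". So some men could overlap. But that study concerned decisions about prostate cancer screening and had a control group, so only some of the 240 had peer-led sessions, and on a different decision. Its funding ended in September 2018, and enrolment here was planned from April 2020, about 18 months later. Shared educators and outreach do not show that any participant overlaps. Focus-group men, by contrast, discussed genetic testing itself and helped shape the intervention, so their exclusion is no precedent for this group.

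**Conclusion.** The gap is real but modest. Nothing in the eligibility criteria, recruitment or baseline passages keeps out, or is stated to identify, a man who has already had germline testing, and the primary outcome, intentions and uptake do not mean the same thing for him.

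Power falls from about 89% to roughly 86–87.5% if 5% of men are affected and show no change, and to roughly 82–85.5% if 10% are. These figures rest on assumed shares, on SD 0.76 applying to change scores, and on no response at all from tested men. The true loss could be smaller.

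A reader might infer that the comparison is biased. It should not be: randomisation balances prior testing in expectation, so the effects are dilution and unclear outcome meaning. A reader might also picture a far larger loss, such as power of 73% with 20% of men affected. That needs a share which nothing in the documents supports, and it holds the SD fixed while assuming zero change. With the step 3 variance, even 20% would leave about 81% (difference 0.32, pooled SD 0.689).

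**What to change.** Add one question to the existing screening call: has the man ever had germline genetic testing for inherited cancer risk? Add to section 4.1.2 (Aim 2/3) that men who answer yes are not eligible. Still count any such man found at screening when describing the proportion who meet NCCN criteria, so that the exclusion does not lower that estimate unnoticed.

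If enrolment is under way, record prior testing at baseline and pre-specify a sensitivity analysis of the primary outcome, intentions and uptake without these men.

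Keep men who were only counselled and men from PC140667 eligible. Record both exposures at baseline as covariates for exploratory analysis.

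The cost is one screening question, two baseline items and a marginally smaller pool. Recruitment is already demanding, at about 2000 men screened for 176 places, but few men should be lost. The results would then apply to men not yet tested, which is the group the hypothesis concerns.
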